4.1 General Design

This is a randomized, open-label phase I/II study. Subjects will be randomized in a 1:1 ratio to receive FLT3 ligand, anti-CD40 antibody, and SBRT (Arm 1) versus standard care (Arm 2). Subjects on either study arm with limited disease will receive SBRT to all evident sites of active disease. Subjects on Arm 1 with extensive disease will initially receive SBRT to a single site of disease but may receive additional “cycles” of FLT3 ligand, anti-CD40 antibody, and SBRT at later time points. Subjects on Arm 2 with extensive disease are expected to receive some form of standard systemic therapy (e.g., docetaxel). Subjects on Arm 2 with limited disease may also receive standard systemic therapy following completion of SBRT to all sites of evident disease, at the discretion of the treating physicians. All subjects will be followed closely for treatment-related toxicities. Whole-body PET/CT and CT imaging will be performed prior to study entry, and restaging CT will be performed every 8 weeks thereafter.

In the phase I component of this study, subjects will be randomized between study arms until 6 subjects have been randomized to Arm 1. Study accrual will then be halted until 8 weeks after the last study subject begins treatment.

If the pre-specified safety criteria are achieved in the Phase I portion of this study, the study will proceed to phase II. The total sample size (Phase I and Phase II) will be 46 subjects. All 46 subjects will be included in efficacy analyses.

If the pre-specified safety criteria are not achieved in the Phase I portion of this study, the investigators and Celldex will review safety data from this trial as well as other trials using CDX-301 and CDX-1140 and determine if the experimental treatment regimen should be altered (e.g., by reducing the CDX-1140 dose). The study protocol would be amended accordingly, and Phase I component with the new treatment regimen would be added.

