5.2.2 Treatment Schedule

CDX-301 and CDX-1140 will only be administered to subjects on Arm 1. Subjects on Arm 2 will not “crossover” if disease progression is observed. The Study Calendar (Section 4.2) describes the timing of study drug administrations.

Some subjects on Arm 1 may receive more than one “cycle” of CDX-301, CDX-1140, and SBRT (targeting a lesion not previously treated with SBRT). The decision to administer treatment cycles beyond cycle 1 must be agreed upon by the treating physicians, the principal investigators, and the study subject. Additional treatment cycles will not be offered to subjects who develop disease progression within four months of receiving a previous cycle of study therapy or to subjects who have no evidence of active disease. Subjects who previously experienced DLT or intolerable toxicity related to CDX-1140 may be treated with CDX-301 and SBRT and without CDX-1140 in subsequent treatment cycles.

For subjects who receive more than one cycle of study therapy, the schedule of events will reset at the beginning of each cycle. At least 8 weeks must separate the start of each treatment cycle.

CDX-301

Five injections of CDX-301 should be administered daily during Week 1 (Monday-Friday) of a treatment cycle. If that is not possible due to department closure for a national holiday, inclement weather, or another reason that is not treatment-related toxicity, CDX-301 treatment may extend to Week 2 (though not beyond 10 days after the first CDX-301 dose).

CDX-1140

The first CDX-1140 will take place 4 days (+/- 1 day) after the last dose of CDX-301. As CDX-301 will typically be given from Monday-Friday, CDX-1140 will usually be given on a Tuesday. The second dose of CDX-1140 will be given 4 weeks (+/- 3 days) after the first CDX-1140 dose. CDX-1140 will not be administered on a Friday, as a clinic visit the day after each CDX-1140 dose is required.

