8.0 STATISTICAL CONSIDERATIONS

8.1 Randomization Procedure

At the time of study registration, subjects will be stratified by EGFR/ALK mutation status and disease burden and then will be randomized 1:1 between the two study arms using a modified permuted block treatment allocation scheme¹¹⁵. Block sizes of 2 (65%) and 4 (35%) will be considered. Study subjects and study personnel will NOT be blinded with respect to the randomization result.

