8.4 Secondary Endpoints and Exploratory Analyses

Overall survival (OS) rates and median OS durations will be estimated using the Kaplan-Meier method. Exploratory comparisons of OS distributions between study arms will be performed using a two-sided log-rank test and Cox proportional hazards models.

Radiographic response rates will be characterized using descriptive statistics. The clinical benefit rate (CBR) will be defined as the percentage of subjects who achieve best response of confirmed CR or PR, or stable disease (SD) for at least four months. CBR in Arm 1 and Arm 2 will be compared using chi-square testing or Fisher

exact test, as appropriate. Objective response rate (ORR) will be defined as the percentage of subjects who do not receive comprehensive SBRT who achieve best response of confirmed CR or PR. ORR in Arm 1 and Arm 2 will be compared using chi-square testing or Fisher exact test, as appropriate.

Quality-of life (QoL) will be assessed using the EORTC QLQ-C30 and EORTC QLQ-LC13. Summary statistics (mean, standard deviation, median, 25th and 75th percentiles, and range) and the mean change from baseline of linear-transformed scores will be reported for all the items and subscales of the EORTC QLQ-C30 questionnaire and the QLQ-LC13, according to the EORTC scoring manual guidelines and the. Completion and compliance rates will be summarized at each timepoint by treatment arm. Only patients with a non-missing baseline assessment and at least one non-missing post-baseline assessment will be included in the analyses.

Daily step count averages at baseline and at various timepoints after study registration will be characterized using descriptive statistics. To test the hypothesis that study therapy preserves physical function compared to standard therapy, a linear mixed effects model with random coefficients using a restricted maximum likelihood procedure will be used to model daily step count as a function of study arm, using adjustment variables such as age and gender.

Exploratory multivariable and subgroup analyses of PFS and OS predictors will be performed. Adjustment/grouping variables will include baseline disease burden, performance status, NSCLC subtype, and prior response to immunotherapy.

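### ORR is compared between arms among subjects who did not receive comprehensive SBRT, when the matching group, the extensive-disease stratum, is already recorded before randomisation

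*Combined protocol and SAP*

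**What the plan says.** Section 8.4 defines ORR as the "percentage of subjects who do not receive comprehensive SBRT who achieve best response of confirmed CR or PR" and adds that "ORR in Arm 1 and Arm 2 will be compared using chi-square testing or Fisher exact test, as appropriate". No response rate, sample size or power is given for ORR.

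Section 8.1 states that "subjects will be stratified by EGFR/ALK mutation status and disease burden and then will be randomized 1:1 between the two study arms". The Section 4.0 design notes describe the disease-burden factor as limited disease, meaning suitable for comprehensive SBRT, against extensive disease. Section 8.1 also says "Study subjects and study personnel will NOT be blinded with respect to the randomization result".

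Section 4.1 links stratum to planned treatment: "Subjects on either study arm with limited disease will receive SBRT to all evident sites of active disease". Extensive-disease subjects on Arm 1 "will initially receive SBRT to a single site of disease but may receive additional" cycles later. Section 6.0 lets extensive-disease subjects on Arm 2 have palliative radiotherapy, which may include SBRT, at the discretion of their physicians.

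Section 8.4 lists baseline disease burden as a grouping variable for the exploratory PFS and overall survival analyses. It does not use that variable to define the ORR population. No section says how a subject counts for ORR when the SBRT received differs from what the stratum implied.

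**The concern.** Excluding comprehensively irradiated subjects from ORR is sensible, because shrinkage of an irradiated lesion says little about systemic effect. The difficulty is that the exclusion depends on what was received. A subject's stratum is fixed before allocation. Whether SBRT to all sites was started and finished is known only afterwards, when patient and physician know the arm.

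A limited-disease subject who deteriorates, declines, or stops before all sites are treated did not receive comprehensive SBRT. On the plain wording that subject joins the ORR denominator, perhaps with some lesions already irradiated. This can happen on either arm, and nothing guarantees that it happens equally often or for the same reasons on both.

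Membership of the compared groups could then depend on events after randomisation, and the ORR difference would lose the protection of randomisation. Groups this small leave little room for that.

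**Working it through.** **The plan's own figure.** None is stated for ORR. The only efficacy power is 81% for PFS (Section 8.3), and it reproduces. Inputs: medians 10 and 5 months, 24 months of accrual plus 12 of follow-up, 23 per arm, two-sided alpha 0.20. With λ = ln 2 / median, the event probability is 1 − (e^(−12λ) − e^(−36λ)) / (24λ), which gives 0.788 and 0.945. Expected events are 23 × (0.788 + 0.945) = 39.9. Power = Φ(√(39.9/4) × ln 2 − 1.282) = 81.8%. None of this uses the ORR set, so the ORR definition cannot affect it.

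**Do the two sets match?**

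| Subject | In extensive stratum | In ORR set as written |
|---|---|---|
| Limited, SBRT to all sites completed | No | No |
| Limited, SBRT not started or not completed | No | Yes |
| Extensive, treated as planned | Yes | Yes |
| Extensive, all sites eventually irradiated | Yes | No, if comprehensive is read cumulatively |

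Row 2 follows from the plain wording. Row 4 needs a particular reading, taken up under the objection.

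**Size.** The stratum split and response rates are not in the plan, so every count here is an assumption. Take n extensive-disease subjects per arm (8, 12 or 16 of 23), with 3 responders in each arm, so that the stratum-based difference is zero. Let k limited-disease subjects on Arm 2 fail to complete SBRT and enter the denominator. Arm 1 stays at 3/n. Arm 2 becomes 3/(n + k) if they are non-responders, or (3 + k)/(n + k) if shrinkage of irradiated lesions makes them responders.

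| n | k | Arm 1 | Arm 2, non-responders added (difference, Arm 1 − Arm 2) | Arm 2, responders added (difference) |
|---|---|---|---|---|
| 8 | 1 | 3/8 = 37.5% | 3/9 = 33.3% (+4.2) | 4/9 = 44.4% (−6.9) |
| 8 | 2 | 37.5% | 3/10 = 30.0% (+7.5) | 5/10 = 50.0% (−12.5) |
| 12 | 1 | 3/12 = 25.0% | 3/13 = 23.1% (+1.9) | 4/13 = 30.8% (−5.8) |
| 12 | 2 | 25.0% | 3/14 = 21.4% (+3.6) | 5/14 = 35.7% (−10.7) |
| 16 | 1 | 3/16 = 18.8% | 3/17 = 17.6% (+1.1) | 4/17 = 23.5% (−4.8) |
| 16 | 2 | 18.8% | 3/18 = 16.7% (+2.1) | 5/18 = 27.8% (−9.0) |

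If the non-completers are on Arm 1 instead, the signs reverse.

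**Adding the less plausible route.** Suppose also that two Arm 1 extensive-disease subjects leave the set, with two non-responders joining Arm 2:

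- n = 12: 3/10 v 3/14 (+8.6 points) if those leaving are non-responders; 1/10 v 3/14 (−11.4) if they are responders.
- n = 8: 3/6 v 3/10 (+20.0) or 1/6 v 3/10 (−13.3).
- n = 16: 3/14 v 3/18 (+4.8) or 1/14 v 3/18 (−9.5).

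In every case shown, in the table and in this list, the two-sided Fisher p-value is above 0.6. The effect is on the estimate, not on a significance call.

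**The case against.** The strongest reply is that the set is in effect fixed before allocation. Comprehensive SBRT is this protocol's treatment for limited disease, suitability for it defines the stratum, and Sections 2.7 and 4.1 say that suitable subjects will receive it on either arm. Under the plan, those who do not receive it are the extensive stratum, and only departures from plan separate the two. This stands. It limits the problem to non-adherence, for which the documents give no rate. Section 5.1.2 lets an interrupted course run past Week 1, so interruption alone does not reclassify anyone.

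A reader might go further and infer that Arm 1 subjects who do well are steadily removed from ORR through repeat cycles, since "Additional treatment cycles will not be offered to subjects who develop disease progression within four months of receiving a previous cycle of study therapy", while Arm 2 has no comparable path. The documents do not support that:

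- Section 4.1 contrasts SBRT to all sites with single-site SBRT plus later cycles, and nowhere calls the latter comprehensive.
- Section 4.2.2 has each repeat cycle treat an untreated lesion, with cycle starts at least 8 weeks apart. Six lesions treated one per cycle would need at least 5 × 8 = 40 weeks to reach the sixth cycle.
- Section 5.1.4 says subjects classed as extensive because of an oversize lesion will not have every active lesion irradiated.
- Section 5.2.2 also withholds further cycles from subjects without active disease, so complete responders cannot leave this way.
- Arm 2 does have a route to later SBRT, the palliative radiotherapy in Section 6.0.

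The route is conceivable, for example for a partial responder with few remaining active lesions, but only if comprehensive is read cumulatively over cycles.

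It is also fair to say that the consequence is limited. ORR is an unpowered secondary endpoint. The clinical benefit rate, which includes confirmed responses, is compared in Section 8.4 with no SBRT exclusion.

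**Conclusion.** The point holds in a limited form. Section 8.4 defines a between-arm comparison by treatment received although an equivalent baseline group exists, and gives no rule for subjects whose treatment departs from their stratum. The clear route to a mismatch is a limited-disease subject, on either arm, whose SBRT to all sites is not started or not completed.

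Under assumed counts of 8 to 16 extensive-disease subjects and 3 responders per arm, one or two such subjects on one arm shift the ORR difference by about 1 to 12.5 points. Adding the less plausible departures from the set widens this to about 20 points at the extreme. These figures illustrate sensitivity; they do not predict a bias.

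Two stronger conclusions should not be drawn. The definition cannot be said to favour one arm, because the direction depends on who is reclassified and whether they respond. Nor does it touch the trial's main conclusions: Section 4.1 puts all 46 subjects in the efficacy analyses, and the 81% PFS power does not depend on the ORR set. The change is worth making because it preserves the intended population at almost no cost.

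**What to change.** Replace the ORR population in Section 8.4 with wording such as: ORR will be assessed in all subjects randomised in the extensive-disease stratum, as recorded at registration, analysed by assigned arm regardless of SBRT subsequently received. Keep the set that did not receive comprehensive SBRT as a sensitivity analysis. For that set, state whether comprehensive refers to the initial course only or accumulates over cycles, and how an incomplete course counts.

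The cost is a few lines of text. The stratum is already recorded, and no new data, sample size or treatment change is needed. There is one small downside: if an extensive-stratum subject later has all sites irradiated, shrinkage of irradiated lesions could count as response. The sensitivity analysis would show whether that matters.

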9.0 REGULATORY CONSIDERATIONS

9.1 Protection of Human Subjects

The Investigator must ensure that patients or their legally acceptable representatives are clearly and fully informed about the purpose, potential risks and other critical issues regarding clinical trials in which they volunteer to participate. Preparation of the consent form is the responsibility of the Investigator and must include all elements required by CFR 21 Part 50.25 and the local IRB.

9.2 Compliance with the Protocol and Protocol Revisions

The study must be conducted as described in this approved protocol. All revisions to the protocol must be provided to the PI. The PI should not implement any deviation or change to the protocol without prior review and documented approval/favorable opinion from the IRB/IEC of an Amendment, except where necessary to eliminate an immediate hazard(s) to study patients. The investigator must ensure that patients or their legally acceptable representatives are clearly and fully informed about the purpose, potential risks and other critical issues regarding clinical trials in which they volunteer to participate. Preparation of the consent form is the responsibility of the PI.

10.0 DATA HANDLING AND RECORD KEEPING

10.1 Confidentiality

Information about study subjects will be kept confidential and managed according to the requirements of the Health Insurance Portability and Accountability Act of 1996 (HIPAA). Those regulations require a signed subject authorization informing the subject of the following:

- What protected health information (PHI) will be collected from subjects in this study
- Who will have access to that information and why
- Who will use or disclose that information
- The rights of a research subject to revoke their authorization for use of their PHI. In the event that a subject revokes authorization to collect or use PHI, the investigator, by regulation, retains the ability to use all information collected prior to the revocation of subject authorization. For subjects that have revoked authorization to collect or use PHI, attempts should be made to obtain permission to collect at least vital status (i.e. that the subject is alive) at the end of their scheduled study period.

10.2 Source Documents

Source data is all information, original records of clinical findings, observations, or other activities in a clinical trial necessary for the reconstruction and evaluation of the trial. Source data are contained in source documents Examples of these original documents, and data records include: hospital records, clinical and office charts, laboratory notes, memoranda, subjects' diaries or evaluation checklists, pharmacy dispensing records, recorded data from automated instruments, copies or transcriptions certified after verification as being accurate and complete, microfiches, photographic negatives, microfilm or magnetic media, x-rays, subject files, and records kept at the pharmacy, at the laboratories, and at medico-technical departments involved in the clinical trial.

10.3 Case Report Forms

The study case report form (CRF) is the primary data collection instrument for the study. All data requested on the CRF must be recorded. All missing data must be explained. If a space on the CRF is left blank because the procedure was not done or the question was not asked, write "N/D". If the item is not applicable to the individual case, write "N/A". All entries should be printed legibly in black ink. If any entry error has been made, to correct such an error, draw a single straight line through the incorrect entry and enter the correct data above it. All such changes must be initialed and dated. DO NOT ERASE OR WHITE OUT ERRORS. For clarification of illegible or uncertain entries, print the clarification above the item, then initial and date it.

10.4 Data Safety and Monitoring Board

The Albert Einstein College of Medicine/Albert Einstein Cancer Center Data Safety Monitoring Committee (DSMC) has the responsibility for ensuring data and

safety monitoring along with the PI who is ultimately responsible for the ongoing monitoring and safety of clinical protocols. The primary functions of the AECC DSMC are as follows:

1. To review and ensure protocol compliance with dose escalation in phase I trials
2. To review/assure protocol compliance for all trials that have two-stage phase II designs,
3. Reviewing all internal and external serious adverse reports, investigator alerts, action letters, and other safety reports for trials being performed at AECC-affiliated institutions and;

To implement and to determine the adequacy of DSM plans of all approved protocols.

The DSMC is an independent committee and meets on a bimonthly basis. During its bimonthly meeting, the DSMC will review serious (grade 3 or higher) adverse events from this study. In the event that the DSMC decides that a protocol revision is warranted, the committee will immediately notify the principal investigator of this study. The DSMC has the authority to close trials to patient accrual should the risk to patients be excessive or outweigh the potential benefits of the study. All study suspensions and closures will be forwarded to the IRB/CCI and study sponsor from the DSMC. The DSMC will review all safety data from Phase I before the study proceeds to Phase II.

11.0 ADVERSE EVENTS

An adverse event (AE) is any untoward medical occurrence in a subject administered a study treatment. An AE can therefore be any unfavorable and unintended sign (including an abnormal laboratory finding), symptom, or disease temporally associated with the use of a study treatment, whether or not related to the study treatment. All observed or volunteered AEs regardless of suspected causal relationship to the study treatment will be reported as described in the following sections. For the purposes of this current study, "study treatment" is defined as CDX-1140, CDX 301, and radiotherapy. AEs for subjects on arm 2 who receive standard therapy (e.g., chemotherapy) will also be reported.

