7.0 SUBJECT ASSESSMENTS

7.1 Clinical Assessments

Clinical assessments will take place according to the schedules depicted in the Study Calendars (Section 4.2) and will include complete histories and physical examinations. History and physicals may be obtained remotely. Additional visits may take place, and events that are noted at those visits (e.g., treatment-related toxicity) will be included in data analyses.

Adverse events will be scored at each clinic visit using CTCAE version 5.0. Any new or worsening toxicities will be classified as “unrelated” or “related” to study treatment (See Section 11.1). Adverse events will be documented in this manner for subjects on both study arms, so that adverse event rates with study therapy in Arm 1 can be compared to adverse event rates with standard therapy in Arm 2.

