8.2 Phase I Primary Endpoint – Dose-Limiting Toxicity

A stopping rule for safety will be implemented as follows: After 6 subjects are randomized to Arm 1 (which will take place after approximately 12 total subjects are enrolled), accrual will be temporarily suspended for DLT monitoring. 8 weeks after the 6th subject on Arm 1 starts treatment, the study will proceed to Phase II if no more than one out of six subjects on Arm 1 has experienced a DLT (defined in Section 7.2).

If the pre-specified safety criteria are not achieved in the Phase I portion of this study, the investigators and Celldex will review safety data from this trial as well as other trials using CDX-301 and CDX-1140 and determine if the experimental treatment

regimen should be altered (e.g., by reducing the CDX-1140 dose). The study protocol would be amended accordingly, and Phase I component with the new treatment regimen would be added.

At the conclusion of the trial, study therapy will be considered safe and worthy of further study if no more than 4 out of 23 subjects on Arm 1 experience a DLT. The target Grade 3 toxicity rate is no more than 12.5%, and a toxicity rate greater than 35% is considered clinically unacceptable. This design has the following operating characteristics: The probability of accepting the treatment for further study if the true toxicity rate is unacceptably high (>35%) is at most 5%. In contrast, there is at least an 85% probability of accepting the treatment for further study if the true toxicity rate is less than 12.5%.

The proportion of patients on Arm 1 who develop a DLT will be computed, along with Clopper-Pearson 95% exact confidence intervals. Frequencies of specific treatment-related adverse events (including delayed adverse events) and event grades will be characterized using counts and percentages.

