11.1 Adverse Event Definitions

Adverse Event (AE): any new, undesirable medical experience or change of an existing condition that occurs during or after treatment, whether or not considered product-related.

Serious Adverse Event (SAE): An AE occurring at any dose that results in any of the following outcomes (CFR 312.32)

- Death
- Life-threatening adverse experience
- Inpatient hospitalization or prolongation of existing hospitalization excluding those for study therapy administration, transfusional support, disease staging/re-staging procedures, thoracentesis / paracentesis, or placement of an indwelling catheter, unless associated with other serious events
- Persistent or significant disability or incapacity
- Congenital anomaly / birth defect.

The definition of SAE also includes important medical event. Medical and scientific judgment should be exercised in deciding whether expedited reporting is appropriate in other situations, such as important medical events that may not be immediately life-threatening or result in death or hospitalization but may jeopardize the patient or may require intervention to prevent one of the other outcomes listed in the definition above. These should also usually be considered serious. Examples of such events are intensive treatment in an emergency room or at home for allergic bronchospasm; blood dyscrasias or convulsions that do not result in hospitalization; or development of drug dependency or drug abuse. A new diagnosis of cancer during the course of treatment should be considered an important medical event.

Causality: the relationship of each AE to study drug will be defined as “unrelated” or “related” to study treatment using the following definitions:

- **Unrelated:** There is little or no possibility that the study treatment(s) caused the reported AE; and other factor(s) including concurrent illnesses, progression and expression of the disease state, concurrent medications, or a reaction to concurrent medications appear to explain the AE.
- **Related:** There exists at least a reasonable possibility that the study treatment(s) caused or contributed to the AE; an inability to identify an alternate etiology for an AE should not, by itself, justify a “related” attribution.

Unexpected Adverse Event: An AE that is not mentioned in the Investigator's Brochure or package insert or the specificity or severity of which is not consistent with the investigator's brochure or package insert.

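### Adverse events caused only by Arm 2 systemic therapy are coded as unrelated, so any between-arm comparison of treatment-related events would undercount Arm 2

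*Combined protocol and SAP*

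**What the plan says.** Section 7.1 grades adverse events by CTCAE version 5.0 at each clinic visit. It classes each new or worsening toxicity as related or unrelated to study treatment and refers to Section 11.1 for the definitions. It continues: "Adverse events will be documented in this manner for subjects on both study arms", and gives the purpose: "so that adverse event rates with study therapy in Arm 1 can be compared to adverse event rates with standard therapy in Arm 2".

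Section 11.0 states that study treatment "is defined as CDX-1140, CDX 301, and radiotherapy". It requires all adverse events to be reported whatever their suspected cause, and adds: "AEs for subjects on arm 2 who receive standard therapy (e.g., chemotherapy) will also be reported".

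Section 11.1 offers two causality categories, both tied to study treatment:
- *Related*: "There exists at least a reasonable possibility that the study treatment(s) caused or contributed to the AE".
- *Unrelated*: "There is little or no possibility that the study treatment(s) caused the reported AE", with some alternative explanation for the event. The listed alternatives end with "concurrent medications, or a reaction to concurrent medications appear to explain the AE".

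Section 8.2 is the only part of Section 8 with a sentence on adverse event frequencies. It says "Frequencies of specific treatment-related adverse events" and event grades will be given as counts and percentages.

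Under Sections 4.1 and 6.0, Arm 2 subjects with extensive disease are expected to receive standard systemic therapy; docetaxel, pemetrexed and gemcitabine are named. The Arm 2 calendar (4.2.3) requires SBRT only for limited disease.

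**The concern.** The classification in 7.1 is there to support a comparison of the two arms, but the definition it relies on covers the whole Arm 1 regimen and only part of the Arm 2 treatment. Harm from CDX-301, CDX-1140 or SBRT can be scored as related. Harm from Arm 2 chemotherapy cannot.

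This gives a one-sided error in any table of related events by arm. The Arm 2 count is too low, and the experimental regimen looks more toxic against standard care than it is. Assignment is open-label (Section 8.1), so investigators will know when an event follows chemotherapy. Some may apply the definition literally while others score the event as related because it is plainly drug-caused. Arm 2 attribution could then be inconsistent as well as biased.

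**Working it through.** The documents give no figure for the between-arm toxicity comparison, so there is nothing to reproduce. The check is to apply the definitions in 11.0 and 11.1 to each kind of subject the protocol allows.

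| Subject | Treatment received | Event caused only by systemic therapy | Event radiotherapy may have caused or contributed to |
|---|---|---|---|
| Arm 1 | CDX-301, CDX-1140, SBRT | Study-drug event: can be related | Can be related |
| Arm 2, limited disease, SBRT alone | SBRT | Not applicable | Can be related |
| Arm 2, limited disease, SBRT then systemic therapy (6.0) | SBRT and standard drug | Unrelated | Can be related |
| Arm 2, extensive disease, systemic therapy with palliative radiotherapy (6.0) | Standard drug and radiotherapy | Unrelated | Can be related |
| Arm 2, extensive disease, systemic therapy only | Standard drug | Unrelated | Not applicable |

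In the last row the subject has received nothing that meets the definition of study treatment, so no event can be related. The statement in 11.0 that Arm 2 events will also be reported ensures they are captured, but supplies no causality rule for them.

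Next, which analyses use this attribution:
- **All-cause rates by arm:** attribution is not used, so there is no effect.
- **Related-event rates by arm:** Arm 2 loses every event caused solely by standard systemic therapy, while Arm 1 loses nothing by definition.
- **Dose-limiting toxicity rules (at most 1 of 6, at most 4 of 23):** these count Arm 1 subjects only, whose protocol treatment is fully covered by the definition. No effect.
- **Progression-free survival:** no effect.

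**Illustration of size.** Arm 2 has 46 / 2 = 23 subjects under 1:1 allocation. Let *f* be the share of Arm 2 given systemic therapy without radiotherapy, and *c* the share of those with an event of interest caused by that therapy. Neither is in the documents; both ranges are assumptions. The number of subjects with a treatment-caused event missing from the related count is 23 × *f* × *c*:

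| *f* | *c* | Subjects missed | Share of Arm 2 |
|---|---|---|---|
| 0.50 | 0.20 | 23 × 0.50 × 0.20 = 2.3 | 10% |
| 0.75 | 0.40 | 23 × 0.75 × 0.40 = 6.9 | 30% |
| 1.00 | 0.60 | 23 × 1.00 × 0.60 = 13.8 | 60% |

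The last row is an outer bound, since it supposes that nobody on Arm 2 receives radiotherapy.

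**The case against.** The strongest reply is that the plan never says the comparison will use related events. Section 7.1 speaks of adverse event rates without that qualifier, and 11.0 reports all events whatever their cause. An all-cause comparison is therefore available and is a natural reading. This stands: a reader might infer that the planned comparison itself miscounts chemotherapy harm, and the documents do not support that. What remains is that no section says the comparison is all-cause, while 7.1 introduces it immediately after the attribution step and extends that step to both arms.

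Section 8.2 is also weak evidence for a related-event comparison. Its sentence on treatment-related events sits in the Phase I dose-limiting toxicity section, follows a sentence about Arm 1, and names no arm. If it covers both arms, the Arm 2 figures are distorted. If it covers Arm 1 only, the comparison in 7.1 has no stated analysis.

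A reader might further infer that the recorded related rate on Arm 2 would be close to zero. That is not supported either. Radiotherapy is within the definition, limited-disease subjects receive SBRT, extensive-disease subjects may receive palliative radiotherapy, and a contribution from radiotherapy is enough for a related score. A rate of zero is forced only in subjects who receive systemic therapy and no radiotherapy.

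Finally, no decision rule depends on the comparison. It is not a listed primary or secondary endpoint (4.3, 4.4) and has no test or threshold. The bias runs against the experimental arm, so it cannot make the regimen look falsely safe. All of this is correct and limits the severity, but it does not make the attribution rule right.

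**Conclusion.** The point holds in a limited form. The rule as written gives the wrong attribution to events caused solely by Arm 2 standard systemic therapy. Any between-arm comparison of treatment-related events would be biased against Arm 1. The events are collected and reported, so they are misattributed rather than lost.

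The direction of the bias follows from the definitions alone. Its size cannot be derived from the documents: the range of 2.3 to 13.8 subjects (10% to 60% of Arm 2) rests entirely on the assumed values of *f* and *c*, and describes only subjects without radiotherapy. The conclusion also assumes that investigators apply 11.0 and 11.1 as written. The wording should be corrected, but no primary analysis or safety decision rule is compromised.

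**What to change.** 1. In 7.1 and 8.2, state that the between-arm comparison of adverse events is all-cause, for any grade and for grade 3 or higher, with treatment-related events as supportive. This needs no new data.
2. In 11.0 and 11.1, add that for the between-arm tabulation Arm 2 events are attributed to the standard therapy received, whether systemic therapy, radiotherapy or both. Record this separately from the investigational-product causality used for serious adverse event reporting (11.2), so that safety reporting to the drug supplier and regulator keeps its present meaning.

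The first change is a sentence. The second adds one attribution entry for Arm 2 events, with no new visits or tests. It is cheap rather than free, because it asks for a causality judgement that the present definition does not collect. That judgement is better made prospectively, since re-attribution later by unblinded investigators would be less reliable.
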